## 6 SAFETY REPORTING

### 6.1 Definition of Adverse Events

Adverse event (AE) is any untoward medical condition or the deterioration of a pre-existing medical condition in a patient or clinical investigation subject administered a pharmaceutical product and which does not necessarily have a causal relationship with the treatment. An AE can therefore be any unfavourable and unintended sign (including an abnormal laboratory finding), symptom, or disease temporally associated with the use of a medicinal product, whether or not related to the medicinal product. An AE may be caused by the use of any medication (e.g. non-indications, combined use), any route of administration, prescription, dose (including overdose) and accidental injuries.

### 6.2 Definition of Adverse Drug Reactions

An adverse drug reaction (ADR), contrary to an AE, is characterized by the suspicion of a causal relationship between the medicine and the occurrence, i.e. judged as being at least possibly related to treatment by the reporter or a reviewing health professional.

An ADR is a response to a medicinal product which is noxious and unintended. This includes adverse reactions which arise from:

- The use of a medical product within the terms of the marketing authorization;
- The use outside the terms of the marketing authorization, including overdose, off-label use, misuse, abuse and medication errors;
- Occupational exposure.

### 6.3 Definition of Unexpected Adverse Drug Reactions

Unexpected adverse reaction refers to a drug reaction whose nature, severity, specificity, or outcome is not consistent with the term or description listed in the current local/regional label. This includes events that may be symptomatically and pathophysiological related to an event listed in the labelling but differ from the event because of greater severity or specificity. For example, under this definition, hepatic necrosis would be unexpected (by virtue of greater severity) if the labelling only referred to elevated hepatic enzymes or hepatitis. Similarly, cerebral thromboembolism and cerebral vasculitis would be unexpected (by virtue of greater specificity) if the labelling only listed cerebral vascular accidents.

"Unexpected," as used in this definition, refers to an adverse drug experience that has not been previously observed (i.e. not included in the label) rather than from the perspective of such experience not being anticipated from the pharmacological properties of the pharmaceutical product.

#### 6.4 Definition of Serious Adverse Events

A serious adverse event (SAE) is defined as any untoward medical occurrence that at any dose that:

- Results in death a
- Is life-threatening b
- Is a congenital anomaly/birth defect c
- Results in persistent or significant disability/incapacity d
- Results in unplanned inpatient hospitalisation or prolongation of existing hospitalisation e
- Is an important medical event that may jeopardise the subject or may require intervention to prevent one of the outcomes listed above f

Further explanations for SAEs are as follows:

- a. Any deaths caused by AEs during the study period, including those that are completely unrelated to the medicinal product. Note: AE terms should be described as the lead cause of death (e.g. multiple organ dysfunction syndrome, pneumonia, myocardial infarction, etc. and with a fatal outcome but not death as an event), with the only exception being unknown causes of death (i.e. sudden or unexplained death), in which case the event term may be "death" or "sudden death".
- b. Life-threatening is an event that places the patient at immediate risk of death from the reaction as it occurred. It does not include a reaction that, had it occurred in a more severe form, might have caused death, e.g. drug-induced liver injury without hepatic failure.
- c. The term refers to any congenital anomaly/birth defect in the offspring of either patient who exposed to the medicinal product.
- d. The term refers to any condition that impairs physical/psychological well-being to the extent that the subject is unable to function normally. Physical disability may include, but is not limited to, permanent disability of locomotion or motility, but also systemic permanent dysfunction as development of heart failure, liver insufficiency or pulmonary fibrosis.

- e. Hospitalisation is defined as at least one overnight formal admission into hospital, usually to perform additional tests, provide treatment that it is not possible to provide at home and/or to allow specific monitoring of the subject due to their unstable medical condition. Hospitalisation for a pre-planned or elective treatment/surgical procedure should not be reported as an SAE unless there are complications or sequelae which meet the criteria for seriousness described above. Hospitalization or prolongation of existing hospitalisation due to non-medical reasons / convenience or purely for the purpose of study does not meet the criteria for medical events and cannot be considered an SAE.
- f. Important medical events that may not result in death, be life-threatening, or require hospitalisation may be considered a significant adverse drug experience when, based upon appropriate medical judgment, they may jeopardize the patient and may require medical or surgical intervention to prevent one of the outcomes listed in this definition. Examples of such medical events include allergic bronchospasm requiring intensive treatment in an emergency room or at home, blood dyscrasias or convulsions that do not result in inpatient hospitalisation, or the development of drug dependency or drug abuse.

## 6.5 Collection of Adverse Events

The study will collect all stipulated events reported from signing the ICF to about 37(+2) hours after the first medication. Sponsor will capture any adverse events collected during the subject's remotely contact by pharmacist or hospital staff.

Pharmacist or hospital staff will report any adverse events collected during the subject's remotely contact to Ferring (E-mail: PPD ) within the following timelines:

- 1) Fatal events, whether they are related/unrelated, must inform the sponsor immediately (within 24 hours of the knowledge of the event).
- 2) All other AE reports must be sent to the sponsor within 3 calendar days of knowledge of the event or receipt of significant follow-up information.

## 6.6 Follow-up of Adverse Events

The sponsor will decide on the requirement for any follow-up of AEs persisting after 37(+2) hours after the first medication. Generally, for all ADRs, pharmacist or hospital staff needs to follow up until:

- 1) Sufficient information has been obtained from the reporter;
- 2) The reporter clearly stated that there was no further information or refused to follow up;
- 3) There is no new information after two follow-ups, and further follow-up cannot obtain more information;
- 4) The reporter cannot be contacted more than 3 times on different days. Follow-up records should be kept properly;
- 5) Mails and letters are returned and there are no other contact methods available.

For Fatal SADR, the following information should be collected promptly, includes: verifying, supplementing and improving information on death cases, drug use, occurrence, diagnosis and treatment of adverse reactions; information about drug storage, use, and occurrence of similar adverse reactions from medical institutions; if the subject is transferred for treatment, investigation should be carried out on the transfer treatment. In addition, the subject's medical records, autopsy reports and other information should be collected according to the actual situation. During the investigation process, the quality of the product should also be reviewed, and quality inspection should be carried out if necessary.

## **6.7 Adverse Events Recording during Case Processing**

The sponsor is responsible for case processing. During case processing, AE recording must be based on subject's reliable reporting. For each AE the following variables will be recorded:

- Verbatim;
- Date/time of AE start and stop;
- Relationship to the medicinal product;
- Action taken with regard to the medicinal product;
- Outcome;
- Seriousness;
- Criteria for seriousness (if applicable);
- Date AE met criteria for seriousness (if applicable);
- Date of hospitalisation and discharge (if applicable);
- Date of death and reason (if applicable);
- Autopsy report (if applicable).

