## 2 STUDY OBJECTIVES

The objectives of this drug intensive monitoring study are to monitor and assess the safety profile of Compound Sodium Picosulfate Granules in the real world clinical practice in Chinese population, including:

- Incidence of known ADRs
- Observe occurrence of unexpected AEs/ADRs
- Incidence and risk factors of SAEs/SADRs

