#### 3.3 Bias and Limitations

##### 3.3.1 *Method to Minimize Bias*

In order to limit this potential selection bias in the recruitment of subjects, the recruiter will be required to include all subjects who have been prescribed Ferring Compound Sodium Picosulfate Granules in a naturalistic fashion.

Since the AE information is collected through the report of subjects, while the missing information of AEs due to subjects failing to declare may be immeasurable.

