## 5 STUDY PROCEDURES

The study procedure includes following steps:

1. Provide signed and dated written informed consent form prior to any procedure related to the study.
2. Evaluate subjects agreed to participate in study to make sure they meet inclusion and exclusion criteria.
3. Register eligible subjects and collect subject demographics and characteristics (gender, age, nation, height and body weight).
4. Follow up the eligible subjects 37 (+2) hours after the first medication.

For the subject who experienced AE, the following information will be collected to evaluate the safety profile of Compound Sodium Picosulfate Granules in real-world clinical practice.

- Medicinal information (administration time and dosage) and indication
- Concomitant medications
- Medical history
- Relevant lab test and its result: for the subject who experienced AE, collect relevant lab tests and its results subjects may receive as much as possible
- Safety evaluation

All stipulated events reported from signing the ICF to about 37(+2) hours after the first medication. AE information include the nature, the start date and end date, the relationship to the medicinal product, the seriousness, the outcome, and the use of corrective treatment, etc.

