### **12.3 Subject Information and Consent**

Prior to any procedure related to the study, informed consent must be obtained from subjects. Informed consent can be expressed verbally or in writing, an official ICF must be dated and signed personally by the subject (or witness/legal representative, if applicable).

The investigational personnel will explain the nature, purpose, possible risk and benefit of the study to each subject (or witness/legal representative, if applicable). The subject must be given ample time to consider participation in the study, before the consent is obtained. Each subject will be informed that he/she is completely free to refuse to enter the study or to withdraw from it at any time, without any consequences for his/her further care and without the need to justify their decision. In case the subject decides to withdraw from the study, the data collected up to this point will be used.

Concerning the study data, the subject will accept by signing the ICF that their medical records may be viewed by the sponsor, RA, a mandated auditor and/or the study monitor in compliance with the statement of confidentiality.

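### Section 6.7 rests AE recording on the subject's own report, from one scheduled remote contact. No route is stated to detect serious events in subjects who cannot answer, so SAE incidence may be underestimated.

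*Combined protocol and SAP*

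**What the plan says.** Section 2 lists "Incidence and risk factors of SAEs/SADRs" among the objectives. Four places determine how such an event enters the data.

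- **Timing.** Section 5 has one scheduled follow-up: "Follow up the eligible subjects 37 (+2) hours after the first medication".
- **Route.** Section 6.5: "Sponsor will capture any adverse events collected during the subject's remotely contact by pharmacist or hospital staff". Section 3.3.1 takes the same view of the source: "Since the AE information is collected through the report of subjects".
- **Source rule.** Section 6.7: "During case processing, AE recording must be based on subject's reliable reporting".
- **Deaths.** Section 6.5: "Fatal events, whether they are related/unrelated, must inform the sponsor immediately". The 24-hour clock starts when the event becomes known.

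The variables listed in Section 6.7 include the date and cause of death and the autopsy report. Section 6.6 calls for medical records, autopsy findings and information from medical institutions for a fatal SADR. Section 6.7.5 lets medical examination abnormalities become AEs.

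The safety population (7.2) requires consent and at least some drug intake, but not a completed contact. Disposition (7.3.2) covers consent, intake and site, with no count of subjects reached or not reached.

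**The concern.** The events that matter most for the SAE objective are those most likely to stop a subject answering a call. Section 6.4 counts deaths caused by AEs as SAEs. Section 1.3 lists anaphylactic reaction, seizure, loss of consciousness and confusional state among the known effects. The product is also used before bowel surgery, and Section 6.7.6 requires injuries from examinations or operations to be recorded as AEs.

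If the chance of capture falls as the event becomes more severe, SAE/SADR incidence is understated. The report would not show this, because an unreached subject who took the drug looks the same as one without an event. Section 4.1.1 also lets a legal representative sign the consent form, yet Section 6.7 gives that representative no role as an informant.

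**Working it through.** The plan states no sample size, SAE rate or contact rate, so there is no figure of its own to reproduce. The check has two parts: whether the text gives a route to first detection, and which way any gap would push the estimate.

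**1. Does any provision detect the event, or does each act only once it is known?**

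| Provision | What it does | Detects an unreported event? |
|---|---|---|
| 6.5, fatal events | 24-hour clock from knowledge; the lead-in covers events collected at the remote contact | No |
| 6.6, fatal SADR | Collects records and autopsy findings | No; the case is already known |
| 6.6, repeated contact attempts | Stopping rule for following up reported ADRs | No |
| 6.2 | Says who may suspect causality | No |
| 6.7, death and autopsy fields | Places to store the data | No; and the subject cannot supply them |
| 6.7.5, examination findings | Rules for coding results | Only if staff come to see the result |
| Section 16, follow-up if necessary | Permits further collection | No trigger for an unanswered call |

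No section names a proxy informant for the scheduled contact or sets a number of attempts for it. None requires a record or vital-status check for an unreached subject, or says how such a subject counts in the incidence.

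**2. Direction of the bias (all values assumed).**

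*(a) Subjects who cannot report.* Let f be the share of SAEs that occur in subjects unable to report, and c the share of those captured another way. Then observed / true = 1 − f(1 − c).

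| f | c = 0 | c = 0.5 | c = 1 |
|---|---|---|---|
| 10% | −10% | −5% | 0% |
| 25% | −25% | −12.5% | 0% |
| 50% | −50% | −25% | 0% |

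Example: f = 0.25 and c = 0.5 give 1 − 0.25 × 0.5 = 0.875, a relative bias of −12.5%.

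*(b) Subjects not reached.* Let L be the share not reached and RR their SAE risk relative to those reached.

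- Kept in the denominator as event-free: bias = (1 − L) / [(1 − L) + RR × L] − 1.
- Dropped, for instance because drug intake was never confirmed: bias = 1 / [(1 − L) + RR × L] − 1.

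| L | RR | Kept | Dropped |
|---|---|---|---|
| 2% | 1 | −2% | 0% |
| 5% | 5 | −21% | −17% |
| 10% | 10 | −53% | −47% |

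Example: L = 0.05 and RR = 5 give a denominator of 0.95 + 0.25 = 1.20. Kept: 0.95/1.20 − 1 = −21%. Dropped: 1/1.20 − 1 = −17%.

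The bias is downward if non-contact is linked to serious events, or if unreached subjects count as event-free. It is zero if they are dropped and non-contact is unrelated to SAEs, or if other sources capture every such event.

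**The case against.** The strongest reply is that one loosely worded sentence is being read against its own section. The fields that follow it include death and autopsy data, which no subject can report. Section 6.4 explains how to word a death, 6.7.3 has a fatal outcome, 6.5 sets a clock for deaths whether related or not, and 6.6 goes to records and institutions. Section 6.2 accepts the judgement of the reporter or of a health professional reviewing the case. Hospital staff are among those collecting events, and nothing forbids a relative from answering the call. Sections 3.3.1 and 3.3.2 disclose under-declaration and loss to follow-up, and the study is descriptive.

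Much of this stands. A reader might infer that the plan can record no deaths at all, or that incapacitating events are bound to be lost and SAE incidence driven toward zero. The documents do not support that. They plainly expect some information on deaths and examinations from sources other than the subject, and staff may hear of an event from a relative or in their own hospital. Nor can mild events be assumed fully captured, since 3.3.1 does not exempt them from under-declaration.

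What the reply does not remove is the gap in detection. The safeguards mostly begin after someone knows of the case. The disclosed limitations cover subjects who fail to declare and loss to follow-up in general, not subjects too ill to answer. For some of those at hospital sites, a record check would recover what 3.3.1 treats as beyond measurement.

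**Conclusion.** The point holds as an internal conflict combined with an ascertainment gap. The source rule in Section 6.7 cannot be squared with that section's death and autopsy fields, or with the record-based sources in 6.6 and 6.7.5, and the text must be reconciled. Following the plan as written can under-ascertain SAEs in subjects who cannot answer one remote contact, and the disposition table would not reveal how many subjects that concerns.

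SAE/SADR incidence may therefore be underestimated, by an amount the documents do not allow to be estimated. The percentages in the working show direction and sensitivity only. They rest on assumed values for the share unable to report, the share captured otherwise, the share unreached and their relative risk. The conclusion of downward bias assumes either that failure to answer is linked to serious events or that unreached subjects count as event-free. The change is worth making because it is cheap and removes a contradiction, not because a given loss has been shown.

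**What to change.** 1. **Section 6.7.** Replace the source rule with one that accepts a reliable report from the subject, legal representative, family member, treating clinician or medical record. Add a source flag for each AE.
2. **Section 5.** Take one alternative contact at registration. For a subject not reached, try that contact. At hospital sites, also check the site's own record for admission, procedure complication or death up to 37 (+2) hours.
3. **Sections 7.3.2 and 7.3.3.** Add reached / not reached / reason to disposition. Report SAE incidence among subjects with ascertained status alongside the full safety population.

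**Cost.** There is one extra field at registration, and existing staff make the extra check only for unreached subjects. Sources become mixed, which the flag makes visible. Pharmacy sites may hold no medical record, so ascertainment will differ by site type and the record check is limited to hospital sites. Alternative contacts are third-party personal data. Section 12.3 has the subject accept that "their medical records may be viewed by the sponsor, RA, a mandated auditor and/or the study monitor"; it does not mention a check by site staff. The consent form therefore needs to cover both the alternative contact and that check, and the change goes to the central ethics committee under Sections 10.1 and 12.1.

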### ***6.7.1 Verbatim/Description of AE***

The recording of AEs should use diagnostic terms whenever possible. If the diagnosis cannot be confirmed, AE can be recorded for the symptoms, signs and abnormal examinations. The record should be updated and reported as follow-up information if later diagnosis is confirmed. It should be ensured that each AE verbatim term consists of a single event, and one diagnosis, sign or symptom is an AE.

### ***6.7.2 Time Recording of AE***

The start date of the AE should be the date when the symptoms appear. If the AE is the deterioration of a pre-existing medical condition at the baseline, the start date is the date of the deterioration of the condition in the study. If the AE is new event in the study and upgraded to SAE, the SAE start date is still the original AE start date.

### ***6.7.3 Outcome of AE***

The outcome of the event will be described in terms of:

- **Recovered:** Subject returned to the baseline state.
- **Recovering:** Event has not been fully resolved, but the subject is already in the recovery phase.
- **Not recovered:** Event is ongoing. e.g. irreversible congenital malformation.
- **Recovered with sequelae:** Used only with persistent incapacity/life-long sequelae, e.g. blindness after diabetes mellitus, hemiparesis after stroke.
- **Fatal:** (S)AE stop date is the date of death.
- **Unknown:** Unknown to investigational personnel, e.g. patient lost to follow-up.

If the outcome is “recovered” or “recovered with sequelae” or “fatal” the AE stop date must be entered.

### ***6.7.4 Assessment of AE***

#### **Causality Classification**

Subject will assess causal relationship between the medicinal product and each AE, and answer “yes” or “no” to the question “Do you consider that there is a reasonable possibility that the event may have been caused by Compound Sodium Picosulfate Granules?”

During case processing, the sponsor will also assess the causality. The relationship of an AE with the medicinal product will be classified according to the following:

– **Related:** The AE follows a reasonable temporal sequence from the medicinal administration and cannot be reasonably explained by the subject's clinical state or other factors (e.g. disease under study, concurrent diseases, and concomitant medications). It may be a known reaction to the drug under study or its chemical group or is predicted by known pharmacology and could not be ruled out with certainty.

– **Not related:** The AE does not follow a reasonable sequence from the medicinal product administration or can be reasonably explained by the subject's clinical state or other factors (e.g. disease under study, concurrent diseases, and concomitant medications).

### **Assessment of Expectedness**

The sponsor is responsible for assessment of expectedness.

#### **6.7.5      *Special Situations of AE Recording***

##### **Persistent or Recurrent AEs**

Persistent AEs are events that persist between assessment time points and no remission. During case processing, such events should be recorded only once. The initial date of the event should be recorded. If the event progresses into an SAE, a corresponding update should be made to reflect the situation.

Recurrent AEs are events that have been resolved between assessment time points but then recurred. Each recurrence of an AE should be recorded separately.

